We propose to conduct a randomized controlled trial (RCT) investigating a novel neurosteroid intervention in Gulf War Veterans with GWVI. Research participants will be recruited via Durham VA IRB-approved local advertising (flyers), Durham VA IRB-approved letters (and follow-up phone calls utilizing a Durham VA IRB-approved phone script), Vet Centers, and the VISN 6 MIRECC Post-Deployment Mental Health Data Repository (over 95% of these Registry participants have provided permission to be re-contacted for future research studies; over a quarter of Veterans in this OEF/OIF/OND era Registry are also Gulf War era Veterans), and by referral from the Durham VA, Raleigh CBOC, Greensboro CBOC, and Morehead City CBOC medical and behavioral health care providers. The target number of participants for this study is 140 subjects who complete at least 4 weeks of the study post-randomization (70 subjects per group, randomized to either adjunctive pregnenolone or placebo). Based on our prior investigations with pregnenolone, we conservatively estimate a drop-out rate of 30%. The power analysis for this study in GWVI was conducted under the assumption that 140 participants reach Visit 4 of the study (i.e. 4 weeks post-randomization). With an estimated 30% drop-out rate, we thus anticipate that we will have to randomize approximately 200 participants to achieve this goal.

Enrolled subjects will be 1). Veterans deployed to the Gulf War theater of operations between 1990 and 1991, 2). Gulf War Veterans who report at least 2 of the following 3 symptoms that began in 1990 or thereafter, that have lasted for more than 6 months, and that are present at the time of screening: a) fatigue that limited usual activity, b) musculoskeletal pain involving 2 or more regions of the body, c) cognitive symptoms (memory, concentration, or attentional difficulties by self-report, 3) on a stable medication regimen (no change in past 4 weeks) and no anticipated change in medications during study, 4) Able to provide informed consent for study participation. Only Gulf War era Veterans will be enrolled into this study. There will be no non-Veteran participants enrolled in this study.

RECRUITMENT PROCEDURES

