Pregnenolone 500 mg in divided doses (250 mg BID) for 4 weeks.

Compliance with study drug treatment will be assessed by counting the returned study drug supply. Subjects that fall below 80% compliance at 2 consecutive visits or miss 6 consecutive doses in a row (3 days of study drug) for two consecutive visits should be withdrawn from the study.

Study Timeline:

1. Referred patients and patients responding to IRB-approved advertisements and/or IRB-approved letters with follow-up phone calls (using an IRB-approved phone script) will meet with a member of the research team to discuss the study and the risks and benefits of participation. In addition, patients will be screened for exclusion and inclusion criteria. If subjects are interested in potentially participating in the study, the informed consent document will be discussed with them. Patients will have the option of taking the informed consent with them and discussing the matter with family, friends and/or clinicians. If applicable, the participant's physician or other VA provider will be consulted regarding the patient's appropriateness of the patient's enrollment in the study.
2. Once the informed consent is signed, the subject will proceed to the initial screening procedures. Each participant will receive the MINI diagnostic assessment tool (Mini-International Neuropsychiatric Interview).
3. A licensed physician, nurse practitioner (NP), or physician's assistant (PA) who is clinically privileged at the Durham VA will examine patients prior to randomization to study drug (pregnenolone) or placebo. Patients will have a venous puncture for laboratory/genetic testing (please also the Schedule of Events). Patients will be asked to provide approximately 3.5 tablespoons of blood on the first study visit, and approximately 2.5 tablespoons of blood on Visits #2, 3, 4, 5, 6 and 7. This is a total of approximately 16 tablespoons of blood over the duration of the study. Subjects will receive an ECG at Visits #1 and 6. Patients with clinically significant abnormal physical exam, blood tests, or ECG that preclude safe study participation will be excluded from the study and referred to their primary care provider or appropriate specialist.

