Subjects may be discontinued from the study by the Principal Investigator for the following reasons:

- Subject withdraws consent to participate in the study;
- Subject is noncompliant with procedures set forth in the protocol;
- Subject experiences an AE that warrants withdrawal from the study;
- It is in PI's opinion that it is not in the subject's best interest to continue;
- Other laboratory, medical, or clinical finding for which clinical care should take precedence over study participation.

Adequacy of Protection from Risks

a) **Physical Risk and Subject Safety:** Possible side effects from drawing blood will be attended to as usual in the phlebotomy laboratory. If a subject experiences serious adverse effects from the study medication, it will be discontinued and s/he will be withdrawn from the study. The subject will immediately be referred for appropriate evaluation and treatment. Adverse events (AEs) and serious adverse events (SAEs) will be documented and reported as required by the Durham VA IRB committee, the FDA, and the national VA Data Safety and Monitoring Board. Progress reports summarizing AEs and SAEs will be submitted to the Durham VA IRB and FDA annually, and to the national VA DSMB every 6 months as required. Any SAEs will be rapidly reported as required within the timeframe and guidelines of the Durham VA IRB, the FDA, and the national VA DSMB.

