3. This project will involve independent PhD-level statisticians. [name] will be completely removed from the conduction of the statistical analyses. After clinical trial data are entered by research staff, double-checked, and cleaned, the database will be locked. No statistical analyses will be conducted prior to the locking of the database. Once the data are locked, a completely de-identified copy of the dataset (no PHI) will be sent to independent statisticians. Once the de-identified database is locked, the blind will then be broken by pharmacist [name]. [name] will conduct the statistical analyses (the statistical analysis plan will be determined a priori), and this analysis will be confirmed by an independent statistician.
4. There will be a VA DSMB that will be overseeing this project.
5. [name] will promptly contact the Durham VA IRB Committee, the Durham VA R+D Committee, the VA DSMB, and the ACOS for Research at the Durham VA if a patent is issued or if a licensing agreement is negotiated.

POWER ANALYSIS: PHYSICAL COMPONENT OF THE SF-36 (Primary Endpoint).

Primary Endpoint Hypothesis: Gulf War Veterans with GWVI who were randomized to pregnenolone will demonstrate significantly greater improvements in the Physical Component Score of the SF-36 compared to Veterans randomized to placebo.

Numeric Results for Two-Sample T-Test

Null Hypothesis: Mean1=Mean2. Alternative Hypothesis: Mean1 > Mean2

The standard deviations were assumed to be equal. A prior investigation in Gulf War Veterans with GWVI determined mean baseline standard deviation in the SF-36 Physical Component Summary to be 7.5 (Donta et al 2003). We chose a more conservative SD estimate of 12.5 for this sample calculation. We utilized the baseline SF-36 score from the same investigation (Donta et al 2003) to estimate approximate baseline SF-36 scores in a Gulf War Veteran cohort with GWVI. Consistent with the literature in this area, we utilized a 7-point difference in the SF-36 as a clinically meaningful change from baseline for this sample size calculation (please see attached SF-36 scoring information in Appendix).

[figure not shown]
Power	Allocation		Alpha	Beta	Mean1	Mean2	S1	S2
	N1	N2						
0.71774	42	42	0.05000	0.28226	33.7	40.7	12.5	12.5
0.75708	46	46	0.05000	0.24292	33.7	40.7	12.5	12.5
0.79175	50	50	0.05000	0.20825	33.7	40.7	12.5	12.5
0.82211	54	54	0.05000	0.17789	33.7	40.7	12.5	12.5
0.84855	58	58	0.05000	0.15145	33.7	40.7	12.5	12.5

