0.87147	62	62	0.05000	0.12853	33.7	40.7	12.5	12.5
0.89124	66	66	0.05000	0.10876	33.7	40.7	12.5	12.5
0.90822	70	70	0.05000	0.09178	33.7	40.7	12.5	12.5
0.92276	74	74	0.05000	0.07724	33.7	40.7	12.5	12.5
0.93516	78	78	0.05000	0.06484	33.7	40.7	12.5	12.5
0.94569	82	82	0.05000	0.05431	33.7	40.7	12.5	12.5

Report Definitions

- Power is the probability of rejecting a false null hypothesis. Power should be close to one.
- N1 and N2 are the number of items sampled from each population; they should be small.
- Alpha is the probability of rejecting a true null hypothesis. It should be small.
- Beta is the probability of accepting a false null hypothesis. It should be small.
- Mean1 is the mean of populations 1 and 2 under the null hypothesis of equality.
- Mean2 is the mean of population 2 under the alternative hypothesis. Mean of population 1 is unchanged.
- S1 and S2 are the population standard deviations. They represent the variability in the populations.

Summary Statement

Group sample sizes of 70 and 70 will **achieve 90% power to detect a difference of 7 points** between the null hypothesis that both group means are 33.7 and the alternative hypothesis that mean of Group 2 is 40.7 with estimated standard deviations of 12.5 and 12.5 and with a significance level (alpha) of 0.05000 using a two-sided two-sample t-test. We thus have 90% power to detect a 7-point improvement in the SF-36.

POWER ANALYSIS: PAIN SYMPTOMS (Secondary Endpoint)

[figure not shown]
Secondary Hypothesis #1: Treatment with pregnenolone will improve pain symptoms in Gulf War Veterans with GWVI.

The potential effect of pregnenolone on pain symptoms will be evaluated using several statistical methods. This clinical trial design will compare two randomly assigned groups (adjunctive pregnenolone or placebo) with respect to self-reported pain measured on a 1-10 pain scale. Inclusion criteria for the study require that all participants report pain severity of at least four. Given that pain often presents as long periods of low-level intensity pain punctuated by periods of acute exacerbation, it is likely that the mean pain level for selected participants will exceed four. Thus for power calculations, we assume a baseline mean pain level of six for each group. We assume a standard deviation of 1.0 (as we have little information to support any specific value in this population).

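### Withdrawing low-compliance participants from the whole study loses their Week 8 SF-36 and can bias the Week 8 contrast, most plausibly upwards

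*Combined protocol and SAP*

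**What the plan says.** The compliance paragraph under Study Interventions (Pregnenolone) assesses compliance by counting returned supply. It continues: "Subjects that fall below 80% compliance at 2 consecutive visits or miss 6 consecutive doses in a row" (glossed as three days of drug) "for two consecutive visits should be withdrawn from the study". The consequence is exit from the study, not only from study drug.

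Withdrawal from Study, under Adverse Events and Safety Evaluations, begins: "Subjects may be discontinued from the study by the Principal Investigator for the following reasons". Noncompliance with protocol procedures is one entry, listed apart from withdrawn consent and adverse events. One section therefore says *should* and the other *may*.

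Four other places decide what follows:

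- Study Timeline, item 9: the SF-36 and the secondary scales are given at Visits 2, 4 and 6 only (Weeks 0, 4 and 8).
- Follow-up Plans: after early withdrawal there is one visit, 7 to 21 days later, with vital signs, laboratory tests and the Columbia scale. EKG Monitoring adds an EKG where obtainable. No efficacy scale is listed.
- Statistical Analysis Plan, Missing data: the mixed models rely on data being missing at random. Dropouts are compared with completers. If the assumption looks untenable, the mixed model is still reported, with further description of the treatment effect at withdrawal.
- Subject Recruitment: "The target number of participants for this study is 140 subjects who complete at least 4 weeks of the study post-randomization".

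**The concern.** Compliance is observed after randomisation and may depend on tolerability or on perceived lack of benefit. A rule that ends participation on compliance alone makes the protocol itself a source of missing Week 8 outcomes, including for people who might have agreed to be assessed. The primary hypothesis compares the groups as randomised. If those removed would have done less well on pregnenolone than those who kept taking it, a model that predicts their Week 8 score from those who stayed will lean towards the effect in compliers.

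Participants removed at Visit 4 or 5 will also usually have completed four weeks. They then count towards the target of 140 while contributing no Week 8 value. If 5% to 20% of the 140 were affected, that is 0.05 × 140 = 7 to 0.20 × 140 = 28 people.

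**Working it through.** **The plan's own figures.** Under Power Analysis: Physical Component of the SF-36, the inputs are a 7-point difference, an SD of 12.5 in each group ("We chose a more conservative SD estimate of 12.5 for this sample calculation"), 70 per group, and a test "with a significance level (alpha) of 0.05000 using a two-sided two-sample t-test". The two-sided noncentral t calculation gives 0.90822, exactly the table entry, so the claim to "achieve 90% power to detect a difference of 7 points" reproduces. The recruitment figure does too: 140/(1 − 0.30) = 200. The standard error of a difference on these inputs is 12.5 × √(2/70) = 2.11 points.

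**When the rule can act.** Randomisation is at Visit 2, so the first two post-randomisation counts are at Visits 3 and 4.

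- Low counts at Visits 3 and 4: removal at Visit 4. The Week 4 SF-36 may be obtained; Week 8 is lost.
- Low counts at Visits 4 and 5: removal at Visit 5. Week 8 is lost.
- Low counts at Visits 5 and 6: the Week 8 assessment falls at Visit 6, so it need not be lost.

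If the lead-in count at Visit 2 also applies, removal could come at Visit 3, with no post-baseline SF-36. The text does not say which visits count.

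**Size, under stated assumptions.** The documents give neither the share removed, p, nor the share r of the Week 8 effect kept by those removed. I assume:

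- p is 5% to 20%, equal in both arms, with no other exits;
- the effect in compliers is 3.5 points at Week 4 and 7 at Week 8;
- those removed show 1.75 points at Week 4, which is observed, and 7r at Week 8, which is not;
- the slope of Week 8 on Week 4 is 0.5. This borrows the 0.50 correlation that the plan uses for Tower of London and, for adjacent visits, fits the default AR(1) structure.

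Effect in all assigned = 7(1 − p) + 7rp.

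Model estimate = 7 + 0.5 × {[3.5(1 − p) + 1.75p] − 3.5} = 7 − 0.875p.

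Overstatement = 7p(1 − r) − 0.875p, which is 6.125p at r = 0 and 2.625p at r = 0.5.

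| p | Estimate | Effect, r = 0 | Excess | Effect, r = 0.5 | Excess |
|---|---|---|---|---|---|
| 5% | 6.956 | 6.650 | 0.306 (5%) | 6.825 | 0.131 (2%) |
| 10% | 6.913 | 6.300 | 0.613 (10%) | 6.650 | 0.263 (4%) |
| 15% | 6.869 | 5.950 | 0.919 (15%) | 6.475 | 0.394 (6%) |
| 20% | 6.825 | 5.600 | 1.225 (22%) | 6.300 | 0.525 (8%) |

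A large simulation under AR(1) at p = 15%, r = 0 gave 5.97 for the effect and 6.88 for the estimate, in line with the table.

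**Sensitivity.**

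- Full effect kept at both weeks (3.5 and 7): estimate and effect are both 7, so there is no bias.
- Correlation of 0.5 between all occasions, with baseline as covariate: the slope becomes 0.5/(1 + 0.5) = 1/3. At r = 0 the excess is 7p − (1.75/3)p = 6.417p, or 0.32 to 1.28 points.
- Week 4 shows no shortfall: the model has nothing to correct with, and the excess at r = 0 is 7p, or 0.35 to 1.40 points.
- Reversal: if 15% are removed, look like compliers at Week 4, and would have gained 1.5 times the effect at Week 8, the true effect is 0.85 × 7 + 0.15 × 10.5 = 7.525 against an estimate of 7.0.
- No drug effect and the same removal pattern in both arms: simulation showed no bias.

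**The case against.** The strongest reply is that the size is unknown and may be small. The rule also catches people just under 80%, who may keep much of any benefit. At half retained, the excess is at most about 0.53 points, against a standard error of 2.11. The SAP does compare dropouts with completers, and Week 4 data carry some of the lost information. All of this stands and limits the size. It does not restore the missing Week 8 values, and no sensitivity analysis is named.

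It can also be said that the Withdrawal from Study list only sets out general investigator powers, so *may* there and *should* in the compliance paragraph need not conflict. That is a fair reading, but the text leaves open whether removal is expected or optional.

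Four stronger readings are tempting, and the documents do not support them:

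- **Removed participants are replaced.** On post-randomisation counts the rule cannot act before Visit 4, and Subject Recruitment gives an all-cause 30% allowance, not a replacement rule for noncompliance.
- **Consecutive missed doses cannot be known.** Tablet counts do not show them, but Study Timeline item 5 has staff telephone every two weeks to ask about compliance. The gap is that no source is named for this trigger.
- **The second trigger is redundant.** Over 14 days, 6 missed of 28 doses leaves 22/28 = 78.6%, already under 80%. With the six extra days supplied for delayed visits, 34/40 = 85%, and only the second trigger fires.
- **Aim 2 loses its low-exposure participants.** Serum is drawn at every visit from 1 to 6, so samples up to exit and any Week 4 outcome remain. Week 8 data are thinned, not eliminated.

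Nor do the documents give a reason for the rule, so one cannot conclude that safety played no part in it.

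**Conclusion.** The concern holds in conditional form. As written, the plan creates avoidable loss of the Week 8 primary outcome for people removed on compliance at Visit 4 or 5, and relies on missing at random to cover it. The Week 8 contrast can then misstate the effect of assignment. Overstatement is the most plausible direction, because people who take less drug would usually be expected to benefit less.

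For 5% to 20% removed and a 7-point effect in compliers, the illustrative overstatement is about 0.3 to 1.2 points with no retained Week 8 effect, 0.13 to 0.53 with half retained, and zero with all retained at both weeks. These figures rest on assumed noncompliance, retention and correlation; none is the plan's estimate for this endpoint. A reader might infer that a positive result would be an artefact. That does not follow: with no drug effect and like removal in both arms there is no bias. If the rule removes different kinds of people in each arm, the error could go either way.

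**What to change.** Separate compliance with study drug from attendance at assessments.

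- State that participants who meet the compliance criterion and still consent are asked to attend the scheduled Visit 4 and Visit 6 outcome assessments (SF-36 and secondary scales) and are analysed in their randomised arm.
- Add a supportive compliance analysis using pill counts and the serum levels already planned.
- Reconcile *should* in the compliance paragraph with *may* in Withdrawal from Study. Say which visits count, including whether the lead-in count does, and what source identifies consecutive missed doses.

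No position is taken on the compliance threshold or on whether study drug continues.

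The cost is a wording amendment and a little more follow-up of these participants at visits already in the schedule. The estimated effect may be smaller, because it would then include people who took less drug.

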We will assess this hypothesis in the context of a two factor repeated measures mixed model ANOVA, with one between subjects factor with two levels (pregnenolone vs. placebo) and one within subjects factor with three levels (Weeks 0, 4, 8 of treatment post-randomization, which correspond to Visits 2, 4, and 6). This hypothesis will be tested using the treatment-by-time interaction, followed by contrasts in least squares means. These contrasts will examine the difference between the treatments at Weeks 4 and 8 on the changes between least squares means between Week 0 to Week 4, and Week 0 to Week 8 of treatment post-randomization. We will perform several such analyses, one for functional outcome as assessed by the Physical Component of the SF-36 (primary endpoint), and others for secondary endpoints, including: pain symptoms (as assessed by the Brief Pain Inventory), executive functioning (as assessed by the Tower of London test of the BACS), fatigue (as assessed by the Multidimensional Fatigue Inventory), and overall psychological functioning (as assessed by the Global Severity Index of the SCL-90R). The response variable will be change from baseline, and we will use baseline as a covariate. Exploratory outcomes will include the BACS composite score (cognitive symptoms), resilience (as assessed by the Connor-Davidson Resilience Scale), anxiety and depression symptoms (as assessed by the Hospital Anxiety and Depression Scale), PTSD symptoms (as assessed by the PTSD Symptom Checklist), and depression symptoms (as assessed by the Beck Depression Inventory-II scale).

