4. Following the screening visit (Visit 1), all patients will begin a two-week placebo-only lead-in period (prior to randomization at Visit 2). On the day that patients are given the study medication and randomized (and at each visit during the study), a set of vital signs will be done including pulse, blood pressure, and weight. With regard to the study medication, participants will be told that they could be getting placebo (a sugar pill) or active medication (pregnenolone). The subjects will be told that they may be receiving a different dose every two weeks. They will be asked to take the medication twice a day; once in the morning and once in the evening.
5. After a week of the placebo lead-in period, a member of the research team will contact the participant to ask about study medication compliance and to answer any questions. A member of the research team will continue to contact patients by phone every two weeks to ask about compliance to study medication, possible suicidality, and potential adverse events (these telephone check-in contacts will be staggered with in-person patient visits every two weeks; please see also Schedule of Events for details).
6. Subjects will return for a study visit every two weeks. Vital signs will be repeated at each visit. A member of the research team will ask subjects about possible side effects and adverse events (utilizing a structured Adverse Event

Form) and will administer the Columbia Suicide Severity Scale to assess possible suicidality. Patients will be asked to return tablets of pregnenolone or placebo to determine compliance with study medication by pill counting. The subject will be given a new supply of tablets (either pregnenolone or placebo, depending upon random assignment) every two weeks. Patients will receive a laboratory testing (Chem 7, GI panel, CBC) at all study visits. Female patients will also receive a pregnancy test at Visits #1, 2, 4 and 6. TSH, free T4, B12/folate, and a lipid panel will be assessed at Visits #1 and 6. A urinalysis and urine tox screen will be conducted at Visits 1, 2, 4, and 6.

7. At Visits #1 (screening visit), 2 (randomization visit), 3, 4, 5 and 6 (each visit is 2 weeks apart), three extra red-top tubes will be collected for pregnenolone levels and determination of pregnenolone metabolite levels, proteins, and other small molecules. A PaxGene tube and two purple top tubes will be collected at Visit #1 (for genetic analyses).

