8. At Visit 6 (=8 weeks post-randomization), the study medication will be tapered (150 mg BID x 2 days, followed by 50 mg BID x 2 days, followed by study medication discontinuation). Subjects will return 1-2 weeks after Visit 6 for a follow-up visit that includes vital signs, laboratory tests, administration of the CSSRS to assess for suicidality, and adverse event assessment.

9. The WRAT, HADS, and TBI screen will be administered at Visit #1. The SF-36, BAC-A, BPI, MFI, SCL-90, HADS, BDI, PCL, WHODAS, SDS, and CDRS will be administered at Visits #2, 4 and 6. The Adverse Event Scale and CSSR (to assess for suicidality) will be administered at each in-person visit and at each telephone visit.

Randomization and Maintenance of the Blind: Randomization will occur in blocks of 10, and will be conducted by the research pharmacist at the Durham VAMC. Only the research pharmacist will have access to the randomization code during conduction of the study, and the PI and all raters, investigators and other study staff will be blinded during the study. The pharmacist does not participate in assessing any of the primary symptom or side effect dependent variables, and conveys no information about treatment assignment to subjects or staff. Study medication will be dispensed every two weeks. Subjects will be given six extra days of medication in case of a delayed or rescheduled appointment. The blind will be broken only if a medical emergency requires this information. If this occurs, the subject will be withdrawn from the study.

After the study is completed and the last participant leaves the study, the aggregate blinded data will be cleaned (i.e. reviewed for possible outliers that may reflect data entry errors, etc.) and the database will be locked. A de-identified copy of the locked data will be given to our PhD-level statistician for analysis. A de-identified copy of the locked data will also be give to a second statistician for independent replication of the study analyses. The PI will not be involved in study data analyses.

Neurosteroid Quantification:

Gas Chromatography/Mass Spectrometry (GC/MS) Preceded by High Performance Liquid Chromatography (HPLC)

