- v. Clinical worsening of psychiatric assessments (>25% increase in PTSD or depression symptoms over two consecutive visits, as assessed by the PCL and BDI-II) will be discussed with the patient's treating psychiatrist, other mental health care provider, or PCP, and the option of study withdrawal will be discussed with the patient and his/her provider. As always, clinical care will take precedence over study participation.

Laboratory Results:**Procedures for Addressing Abnormal Laboratory Results:**

- i. Patients will receive a CBC, clinical chemistry panel, and liver function tests at each of the six study visits in this clinical trial. At screening, mid-point, and final study visit, patients will also receive a urinalysis and urine toxicology test (and serum pregnancy test if female). At the screening study visit, patients will receive a TSH, B12/folate, and lipid levels. Lipid levels will also be checked at Visit 6. Laboratory results out of the normal range (range determined by the Durham VA Medical Center Clinical Chemistry Laboratory that services both the outpatient and inpatient services at our hospital, and that will conduct the above lab assessments for this study) will receive appropriate review and follow-up as described below.
- ii. The PI (or MD/NP/PA member of the research team supervised by the PI) will review laboratory results within 24 hours. Clinically relevant laboratory abnormalities will receive prompt follow-up attention with the patient's PCP or other health care provider, the internist physician in the ER, and/or a follow-up visit for additional lab work as clinically indicated.
- iii. The DVAMC Clinical Chemistry Laboratory that services the hospital will phone the PI with any "alert" laboratory values that require immediate attention.
- iv. Any laboratory abnormalities that may potentially preclude study participation will be discussed with the patient's PCP, the internal medicine ER physician, the patient's treating psychiatrist, or other relevant health care provider.

EKG Monitoring:**Procedures for Addressing Abnormal EKG Findings:**

- i. Final EKG readings issued by a cardiologist are available from the DVAMC Heart Station within 48 hours.

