- ii. Each patient will have an EKG at baseline and completion of the study. If the patient does not complete the study and withdraws prior to the final study visit, every effort will be made to obtain an EKG at the follow-up visit post-withdrawal from the study (please see withdrawal plan below).
- iii. Any abnormal EKG findings will be discussed with cardiologist [name] (former Chair of the Department of Medicine at Duke), who generously consults with our clinical trial team. If [name] suggests

additional medical follow-up, we will proceed according to his recommendations (see below). If [name] is unavailable, the EKG will be discussed with another cardiologist, the ER physician, or the patient's PCP.

iv. Additional potential follow-up actions may include, but are not limited to: Primary care provider notification by pager or VA email, the placement of a cardiology consult, a repeat EKG (if lead placement is suspected to have been suboptimal, for example), or referral to the onsite Acute Care Clinic/Emergency Room for assessment.

Psychiatric Worsening:

Procedure for Addressing Psychiatric Worsening:

i. Patients who demonstrate psychiatric worsening as assessed by a 25% increase over baseline of the PCL (PTSD symptoms) or BDI-II total score (depression symptoms) on two consecutive visits (which are two weeks apart) may be withdrawn from the study (even if this change is thought to be unrelated to the study), and they will be referred to their treating psychiatrist, other mental health care provider, PCP, or the onsite Psychiatric Emergency Care team. Please see also above description.

ii. Patients who exhibit suicidal or homicidal ideation requiring urgent evaluation during a study visit will be referred to the onsite DVAMC Psychiatric Emergency Care team for prompt assessment and possible inpatient psychiatric admission.

Addressing Hormonal Changes in Response to Test Drug or Drug Metabolites:

Procedures for Quantifying Neurosteroid and Neurosteroid Metabolite Levels:

Neurosteroids and neurosteroid metabolites will be quantified by gas chromatography/mass spectrometry (preceded by high performance liquid chromatography), radioimmunoassay, or ELISA, as previously described. Our prior data suggest that pregnenolone, pregnenolone sulfate, progesterone, and allopregnanolone increase following treatment with pregnenolone (please see below for additional detail).

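### The psychiatric-worsening withdrawal rule needs PCL or BDI-II scores two weeks apart, but the scales are scheduled four weeks apart, so it cannot be met before Visit 6

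*Combined protocol and SAP*

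**What the plan says.** Two sections of Additional Safety Plan Details deal with psychiatric worsening.

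- **Psychiatric Worsening, item i.** A 25% increase over baseline in PCL or BDI-II total score is the trigger. Participants who show it "on two consecutive visits (which are two weeks apart) may be withdrawn from the study", even if the change is thought unrelated to the study, and are referred for care.
- **Vital Signs and Side Effect Monitoring, item v.** The trigger here is a ">25% increase in PTSD or depression symptoms over two consecutive visits, as assessed by the PCL and BDI-II". No baseline is named. The consequence is a discussion with the treating provider, including the option of withdrawal.

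The schedule that must supply the scores is set elsewhere.

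- **Study Timeline, item 6:** "Subjects will return for a study visit every two weeks".
- **Study Timeline, item 9:** "BDI, PCL, WHODAS, SDS, and CDRS will be administered at Visits #2, 4 and 6". Visit 1 has the WRAT, HADS and TBI screen.
- **Primary outcome analysis:** "Weeks 0, 4, 8 of treatment post-randomization, which correspond to Visits 2, 4, and 6".
- **Titration schedule:** 100 mg for 2 weeks, 300 mg for 2 weeks, then "Pregnenolone 500 mg in divided doses (250 mg BID) for 4 weeks".
- **Study Timeline, item 8:** "At Visit 6 (=8 weeks post-randomization), the study medication will be tapered". The follow-up visit lists neither PCL nor BDI-II.

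**The concern.** Visits are two weeks apart, but the two scales named in the rule are given at every second visit. The rule's wording assumes a score at each visit, and item 9 of the Study Timeline does not provide one.

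PTSD and depression are permitted at entry (exclusion criterion 11), so worsening of these conditions is foreseeable. The protocol chose an explicit score-based rule for it. An IRB or monitoring board would take the rule as a safeguard during treatment. If the scores it needs do not exist until treatment ends, it gives no protection while participants are on drug.

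The two sections also differ in threshold (25% against more than 25%), in reference point (baseline against none) and in consequence. Staff could handle the same scores in different ways.

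**Working it through.** **Visit map.** Visit 2 is randomization and visits are two weeks apart, so Visit v falls at Week 2 × (v − 2). Doses follow the titration schedule.

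| Visit | Week | PCL and BDI-II scheduled | Dose over the preceding two weeks |
|---|---|---|---|
| 2 | 0 | yes (baseline) | placebo lead-in |
| 3 | 2 | no | 100 mg |
| 4 | 4 | yes | 300 mg |
| 5 | 6 | no | 500 mg |
| 6 | 8 | yes | 500 mg, taper starts |

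The two-week spacing is right for study visits in general. It is wrong for visits at which these scales are given.

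**Can the rule be met?**

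- Gaps between scores: Visits 2 and 4, 4 weeks; Visits 4 and 6, 4 weeks; Visits 2 and 6, 8 weeks. Pairs two weeks apart: 0 of 3.
- Literal reading (adjacent visits two weeks apart): no qualifying pair, so the rule is never met.
- Lenient reading (consecutive post-baseline assessments): the only pair is Visits 4 and 6, so it is first met at Week 8.
- Post-baseline scores before Visit 6: 1, where the rule needs 2.
- Scores taken on 500 mg before Visit 6: 0.

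**With both scales added at Visits 3 and 5.** The qualifying pairs become Visits 3 and 4 (met at Week 4), 4 and 5 (Week 6), and 5 and 6 (Week 8). The earliest trigger is Visit 4.

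**Comparing two remedies.** The documents give no visit-to-visit variability for these scales. I assume a true baseline of 1 and independent normal noise with SD s = 0.10 to 0.20 of the baseline score at every visit including baseline, for one scale. The trigger is a score of at least 1.25 times the observed baseline. A true rise of 40% is likewise an assumption.

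For a single Visit 4 score, the difference between the score and 1.25 × baseline has SD s × √(1 + 1.25²) = 1.6008 s.

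- No true change: 1 − Φ(0.25 / 1.6008 s) = 0.059 at s = 0.10 and 0.217 at s = 0.20.
- True 40% rise: Φ(0.15 / 1.6008 s) = 0.826 and 0.680.

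The two-consecutive-score rule (Visits 3 and 4, or 4 and 5) was simulated with 2,000,000 draws.

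| Chance of firing before Visit 6 | As written | Visits 3 and 5 added, two scores | Single Visit 4 score |
|---|---|---|---|
| No true change | 0% | 3% to 15% | 6% to 22% |
| True 40% rise from Visit 3 | 0% | 80% to 63% | 83% to 68% |

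The first figure in each range is for s = 0.10 and the second for s = 0.20.

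Two checks on this comparison:

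- The rule accepts either scale. If the two scales were independent, false triggers would be 1 − (1 − p)², that is 6% to 28% for the two-score rule and 11% to 39% for the single score. Positively correlated scales would fall between these and the one-scale figures.
- If a 40% rise begins only at Visit 5, the two-score rule fires before Visit 6 in 6% to 21%. Most of that is chance, because its second true score arrives at Visit 6.

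**The case against.** **The schedule may be incomplete.** The Study Timeline refers to a Schedule of Events that is not in the text reviewed, and item 9 does not say that the scales are given at no other visit. The narrative lists do disagree elsewhere: the Study Timeline puts TSH and B12/folate at Visits 1 and 6, while Laboratory Results puts them at screening and adds only lipids at Visit 6. The authors may have meant to give PCL and BDI-II every two weeks. This stands as a reason to check the schedule first. It does not remove the inconsistency: if the schedule does include Visits 3 and 5, item 9 is the text to correct.

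**The companion rule may act earlier.** Psychiatric Worsening item i refers back to the earlier description. Read that way, a rise from Visit 2 to Visit 4 could prompt a discussion of withdrawal at Week 4. This is a fair reading, but the cross-reference does not reconcile the two wordings. The Visit 4 score is also taken before the 500 mg dose has been in use.

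**Other safeguards exist.** Withdrawal under the rule is discretionary. Suicidality and adverse events are checked weekly, and unscheduled appointments are allowed for possible side effects. The investigator may discontinue a participant for "Other laboratory, medical, or clinical finding for which clinical care should take precedence over study participation". No endpoint or power figure depends on the rule. All of this stands and limits the consequence. None of these routes measures a 25% rise in PTSD or depression scores, however.

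**The probabilities rest on assumptions.** They do, and they serve only to compare the remedies. The defect follows from the visit map alone.

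**Conclusion.** The concern holds. On the schedule in the text, the Psychiatric Worsening rule is never met on a literal reading and is first met at Visit 6 on a lenient one. It cannot act during the 8 treatment weeks. This rests on one condition: that the Schedule of Events, which was not available, adds no PCL or BDI-II at Visits 3 or 5. Nothing in the text reviewed places them there.

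The counts describe this rule only. They do not give the chance that a worsening participant would be missed by every other route. This should be corrected because a stated safety rule does not work as scheduled and its two wordings disagree, but it does not threaten the trial's efficacy conclusions.

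**What to change.** First confirm what the Schedule of Events says about PCL and BDI-II.

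**Preferred.** Give PCL and BDI-II at Visits 3 and 5 as well as 2, 4 and 6. The existing rule then works from Visit 4, and Visit 5 supplies a score on 500 mg. The cost is an amendment and 2 scales × 2 visits = 4 extra questionnaires per participant, at most 4 × 200 = 800 forms for the roughly 200 participants to be randomized. One limit remains: worsening that starts on 500 mg gets its second score only at Visit 6, so a rise seen at Visit 5 alone would be handled under investigator discretion.

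**Alternative.** Keep the schedule, remove the two-week condition and trigger on a single post-baseline score at least 25% above Visit 2. This adds no forms. It gives more false triggers under the stated assumptions and still no score on 500 mg before Visit 6.

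**In either case,** give Psychiatric Worsening item i and Vital Signs and Side Effect Monitoring item v the same threshold, the same Visit 2 reference and the same consequence: discussion with the treating provider, referral, and an investigator decision on withdrawal.
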